10.4 PLANNED INTERIM ANALYSES

Each cohort will be analyzed after stage 1 has completed enrollment to conduct the futility analysis. During this time, additional enrollment to that cohort will be halted. The PI will communicate the results of the

analysis to the assigned biostatistician and the Moffitt Protocol Monitoring Committee and make the appropriate determination on resumption of enrollment.

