5.4.1 REASONS FOR WITHDRAWAL OR TERMINATION

Participants are free to withdraw from participation in the study at any time upon request. An investigator may terminate participation in the study in the following circumstances:

- If any clinically adverse event (AE), laboratory abnormality, or other medical condition or situation occurs such that continued participation in the study would not be in the best interests of the participant
- If the participant meets an exclusion criterion (either newly developed or not previously recognized) that precludes further study participation.
- Any subject who becomes pregnant during the study, must be promptly withdrawn from the study and
 discontinue further study treatment. All subjects and female partners of male subjects who become
 pregnant must be followed to the completion/termination of the pregnancy. This is discussed in additional
 detail in section 8.4.5 along with the required reporting guidelines.

If the subject is agreeable, all efforts will be made to continue follow-up of withdrawn or terminated participants, especially for safety and efficacy end-points. All protocol specific safety follow-up procedures to capture adverse events, serious adverse events and unanticipated problems will be made.

The above does not apply to those subjects who come off protocol specific treatment for unequivocal progression of disease. For this group, appropriate follow-up will continue for safety and survival as specified in the protocol.

All subjects who have received at least one dose of CC-122 and/or nivolumab will be included in the safety analysis. Subjects who withdraw during screening after being deemed eligible but have not started protocol specific therapy will be replaced. For patients to be included in the efficacy analysis, they should have received at least 75% of the cumulative dose of CC-122 during cycle 1. If this parameter is not met, they will be replaced after discussion with the study statistician.

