- Obtain demographic information, medical history, and medication history.
- Record vital signs (including weight), results of examinations. Recording of height is necessary only
 at screening or baseline visit
- Collect study specific laboratory/biomarker tests and other studies that are outlined in the Schedule of Events. This also includes standard of care assessments.
- Administer the study treatment (nivolumab plus CC-122; first dose of CC-122 to be administered in the Clinical Research Unit).
- Collect blood for biomarker analysis at 5 hours post CC-122 administration.

Follow-up Visit (Visit 2; C1 Day 15; +/- 2 days)

- Record adverse events as reported by participant or observed by investigator.
- Record vital signs, confirm medical history and perform physical examination
- Collect blood for routine testing and biomarker analysis as specified.
- Administer nivolumab per institutional standard.
- Record participant's adherence to treatment program.
- Schedule/remind subject of follow-up tumor biopsy (same site as done at screening) to be done between days 22 and 29 of cycle 1.

Follow-up Visit (Visit 3; Cycle 2, day 1, +/- 2 days)

- Record adverse events as reported by participant or observed by investigator.
- Record vital signs, confirm medical history and perform physical examination
- Administer nivolumab and provide CC-122 for home use
- Record participant's adherence to treatment program.

Subsequent Visits to follow the 'Schedule of Events' calendar: All scheduled visits have the same window of +/- 2 days. If there is a need to schedule outside of this window, this may be done at the discretion of the principal investigator as long as there is no perceived jeopardy to the health of the participant. Tumor measurements by cross-sectional imaging will be performed every 12 weeks (+/- 7days) unless documented progression or subject taken off the clinical trial. Adverse events as reported by the subject or observed by the investigator will be recorded at each visit.

Final/End of Treatment (EOT) Study Visit

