10 STATISTICAL CONSIDERATIONS

10.1 STATISTICAL AND ANALYTICAL PLANS

This is a phase II study with interim analysis for futility using Simon's two-stage design^{46,47} for the anti-PD1 therapy naïve and refractory subjects as follows:

Cohort 1: Anti-PD1 therapy naïve subjects:

Patients will be treated with CC-122 plus Nivolumab. The primary end point is response rate. The null hypothesis that the true response rate is 40% will be tested against a one-sided alternative of 60%. Targeting 90% power and 10% type I error, 28 evaluable subjects will be enrolled in stage 1 (n=28); if \leq 11 responders by RECIST – further enrollment will be stopped to this arm for futility. Otherwise enrollment will continue for an additional 13 patients in stage 2 for a total cohort sample size of 41 evaluable subjects. The null hypothesis will be rejected if 21 or more responses are observed in 41 patients.

Cohort 2: Anti-PD1 refractory subjects:

This cohort includes subjects who have demonstrated progression on previous anti-PD1 therapy and for whom continuation/resumption of an anti-PD1 agent would not be likely to elicit a radiographic response. Retrospective data using ipilimumab suggest a response of 10% following prior anti-PD1 therapy. For this cohort, we have set the null hypothesis rate to 10% with an alternative hypothesis of 30%. This sample size will be 25 if full accrual (16 patients in stage 1; If 2 or more responses - proceed to full accrual). The null hypothesis will be rejected is 5 or more subjects experience an objective response to therapy. This design yields a type I error rate of 9.5% with a power of 90%.

The maximum number of patients to be enrolled assuming complete enrollment will be 66 (41 + 25); minimum would be 44.

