The trial will be stopped for review if the number of dose limiting toxicities (DLTs) is equal to or exceeds b_n out of n patients with completed follow-up. This is targeting 25% DLT with 25% probability of early stopping for each cohort. For cohort 1, the maximum accrued number of patients will be 41 while the maximum accrued number of patients will be 25.

For cohort 1, the maximum accrued number of patients will be 41. The trial will be stopped if the number of dose limiting toxicities is equal to or exceeds b_n out of n patients with completed follow-up.

Number of Patients, n	1	2	3	4	5	6	7	8	9	10	11	12	13	14	15	16	17	18	19	20
Boundary, b _n	-	2	3	3	4	4	4	5	5	5	6	6	6	7	7	7	8	8	8	9
Number of Patients, n	21	22	23	24	25	26	27	28	29	30	31	32	33	34	35	36	37	38	39	40
Boundary, b _n	9	9	10	10	10	11	11	11	11	12	12	12	13	13	13	14	14	14	15	15
Number of Patients, n	41	42	43	44	45	46	47	48	49	50	51	52	53	54	55	56	57	58	59	60
Boundary, bn	15																			

This boundary is equivalent to testing the null hypothesis, after each patient, that the event rate is equal to 0.25, using a one-sided level 0.09 test.

For cohort 2, the maximum accrued number of patients will be 25. The trial will be stopped if the number of dose limiting toxicities is equal to or exceeds b_n out of n patients with completed follow-up.

```
Number of Patients, n 1 2 3 4 5 6 7 8 9 10 11 12 13 14 15 16 17 18 19 20 Boundary, bn - 2 3 3 3 4 4 5 5 5 5 6 6 6 6 7 7 7 8 8 8 8

Number of Patients, n 21 22 23 24 25 26 27 28 29 30 31 32 33 34 35 36 37 38 39 40 Boundary, bn 9 9 9 10 10
```

This boundary is equivalent to testing the null hypothesis, after each patient, that the event rate is equal to 0.25, using a one-sided level 0.11 test.

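### Does the stage-1 futility analysis need a stated minimum follow-up, given that the first scan comes at about week 12?

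*Combined protocol and SAP*

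**What the plan says.** Section 10.4 (Planned Interim Analyses) gives the trigger: "Each cohort will be analyzed after stage 1 has completed enrollment to conduct the futility analysis". It adds: "During this time, additional enrollment to that cohort will be halted". It states neither how long the halt lasts nor what data must be in hand. The results go to the biostatistician and the institution's monitoring committee before enrolment resumes.

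Section 10.1 sets the rules. For cohort 1, "28 evaluable subjects will be enrolled in stage 1 (n=28"), and the cohort closes with 11 or fewer RECIST responders; otherwise it goes to 41, and 21 or more responses reject the null rate of 40% (alternative 60%). Cohort 2 has 16 patients in stage 1, continues with 2 or more responses, goes to 25, and rejects the null rate of 10% with 5 or more (alternative 30%).

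Section 7.1 fixes the scans: "Tumor measurements by cross-sectional imaging will be performed every 12 weeks (+/- 7days"). The only written condition for entering the efficacy analysis is in section 5.4.1: "they should have received at least 75% of the cumulative dose of CC-122 during cycle 1", with replacement of patients who fall short. The toxicity boundary in section 10.3 counts events "out of n patients with completed follow-up".

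**The concern.** A Simon design has its stated error rates only if the response status of every stage-1 patient is known at the decision. Completed enrolment does not guarantee that: a patient enrolled last has no scheduled scan for about 12 weeks. Evaluability as written rests on cycle-1 dosing, which can be satisfied some eight weeks before that scan, so it does not close the gap. Read literally, a look taken soon after the last enrolment would comply with section 10.4. If patients not yet scanned were then counted as non-responders, the responder count would be too low and a cohort could be closed although the combination works. The cohort 1 boundary of 11/28 (39%) lies almost at the null rate of 40%, so a few uncounted responders matter. The direction of harm is a false stop, not a false claim of activity.

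**Working it through.** **Inputs.** Design constants are from section 10.1, the scan interval from section 7.1, the 75% rule from section 5.4.1 and the dosing pattern (5 days on, 2 off, 28-day cycle) from section 6.1.1. Accrual rates of 1, 2 and 3 patients a month per cohort are assumptions; the documents give none.

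**Step 1: the plan's own figures.** With stage-1 size n1, total n, continuation at r1 or more and rejection at r or more,

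P(reject) = Σ (x = r1 to n1) Bin(x; n1, p) × P[Bin(n − n1, p) ≥ r − x].

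- Cohort 1 (28/41, r1 = 12, r = 21): type I error 0.0951 at p = 0.4, power 0.9009 at p = 0.6. The chance of a false stop is P[Bin(28, 0.6) ≤ 11] = 0.0215.
- Cohort 2 (16/25, r1 = 2, r = 5): type I error 0.0951 at p = 0.1, power 0.9030 at p = 0.3. The chance of a false stop is P[Bin(16, 0.3) ≤ 1] = 0.0261.

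These agree with the plan (10% and 90% targeted in cohort 1; 9.5% and 90% stated in cohort 2).

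**Step 2: the earliest look.** A full cycle has 4 × 5 = 20 CC-122 doses, and 75% of these is 15. The 15th dose falls on day 19 at the earliest, and the cycle ends at week 4. Whether the last stage-1 patient is evaluable or must be replaced is therefore not known until then. From that point to the week-12 scan is 84 − 19 = 65 days (9.3 weeks) down to 12 − 4 = 8 weeks. At 4.345 weeks a month this is 1.8 to 2.1 months of accrual, or about 2, 4 or 6 unscanned patients at 1, 2 or 3 a month.

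**Step 3: the harmful reading.** Suppose m stage-1 patients are unscanned and counted as non-responders at the look, with their later responses counted at the end. Replace n1 by n1 − m in the formula.

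| m | Cohort 1 power | false stop | type I | Cohort 2 power | false stop | type I |
|---|---|---|---|---|---|---|
| 0 | 0.901 | 2.2% | 0.095 | 0.903 | 2.6% | 0.095 |
| 2 | 0.888 | 5.2% | 0.090 | 0.891 | 4.8% | 0.091 |
| 4 | 0.846 | 11.4% | 0.076 | 0.863 | 8.5% | 0.083 |
| 6 | 0.751 | 22.8% | 0.055 | 0.811 | 14.9% | 0.072 |

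A look on the very day of last enrolment would leave about 3, 6 or 8 unscanned (2.76 months × 1, 2 or 3), with cohort 1 power 0.872, 0.751 or 0.587. At that date, however, the number of evaluable patients is not yet established.

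**Step 4: what happens at an early look under the alternative.** With 2, 4 or 6 unscanned in cohort 1, the 12th response is already recorded with probability 1 − 0.052 = 94.8%, 1 − 0.114 = 88.6% or 1 − 0.228 = 77.2%, and the stop rule can no longer be met. In the remaining cases the count is below 12 with patients pending. For example, 10 responders among 24 scanned with 4 pending is not yet a result on 28, and the written rule cannot be applied to it.

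**Step 5: would requiring the first scan secure 90%?** Not by itself. If, as an assumption, 90% or 80% of eventual responses were visible at the look, with everyone scanned, power would be 0.863 or 0.740 in cohort 1 and 0.891 or 0.870 in cohort 2.

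**The case for a change.** The strongest case for a change is that nothing in the text compels waiting. Evaluability is defined by dose only, the halt has no end condition, and section 10.3 shows that the authors thought about data maturity for toxicity but not for response. The trial is open-label with investigator-assessed response, and the investigator takes part in the decision to resume. Closing a cohort is hard to reverse, and one or two sentences would settle the timing at the cost of a pause of at most about 13 weeks.

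It stands that section 10.4 is silent on the cut-off and on how an unscanned patient counts, and that a sentence would do no harm. Three parts carry less weight. The toxicity rule's completed follow-up has no stated length either, so it is not a better-specified standard. An open-ended halt gives room for the scans; without a wait for data there would be little reason to stop accrual. And calling a patient without a scan a RECIST non-responder while that scan is still due is an analyst's choice that the text does not direct. A sentence requiring only the first scan would also leave later responses to judgement, as step 5 shows, so the plan would still depend on the statistician's sense of when the data are mature.

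**Conclusion.** No change is needed. This is a missing cut-off sentence of the kind that analysts fill sensibly: the look comes after enrolment, accrual is halted, and the rule needs the responses of 28 or 16 patients. Applied that way, and with responses visible by the look, the designs have power 0.901 and 0.903, as planned.

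A loss appears only if the look is taken at about week 4 after the last enrolment and pending patients count as non-responders. Its size then depends on accrual. At an assumed 1 a month per cohort it is about 1 point (0.888 and 0.891). At 3 a month it is about 15 points in cohort 1 (0.751) and 9 in cohort 2 (0.811). Type I error falls throughout, so no false claim of activity becomes more likely. None of the three conditions (early look, pending counted as failures, accrual rate) is in the documents, and a loss of power is not shown.

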10.5 SAMPLE SIZE

Details provided above.

11 SOURCE DOCUMENTS AND ACCESS TO SOURCE DATA/DOCUMENTS

The PI and other appropriate study staff are responsible for maintaining appropriate medical and research records for this trial, in compliance with ICH E6 and regulatory and institutional requirements for the protection of confidentiality of participants. Representatives of Celgene and federal regulatory agencies may examine records for the purpose of quality assurance reviews, evaluation of the study safety, progress of the trial, and data validity.

Source documentation in both electronic and paper form shall be retained for at least two years after the final closure of the trial. These include hospital records, clinical research subject charts (with paper AE logs), research laboratory notes, electronic CRFs, and pharmacy dispensing records.

12 QUALITY ASSURANCE AND QUALITY CONTROL

QC procedures will be implemented beginning with the data entry system and data QC checks that will be run on the database will be generated. Any missing data or data anomalies will be communicated to the site(s) for clarification/resolution.

Following written SOPs, the Moffitt Internal Monitors will verify that the clinical trial is conducted and data are generated, documented (recorded), and reported in compliance with the protocol, GCP, and the applicable regulatory requirements (eg, good laboratory practices (GLP), good manufacturing practices (GMP)).

The investigational site will provide direct access to all trial related sites, source data/documents, and reports for the purpose of monitoring and auditing by the sponsor, and inspection by local and regulatory authorities.

13 ETHICS/PROTECTION OF HUMAN SUBJECTS

13.1 ETHICAL STANDARD

The investigator will ensure that this study is conducted in full conformity with Regulations for the Protection of Human Subjects of Research codified in 45 CFR Part 46, 21 CFR Part 50, 21 CFR Part 56, and/or the ICH E6.

13.2 INSTITUTIONAL REVIEW BOARD

The protocol, informed consent form(s), recruitment materials, and all participant materials will be submitted to the IRB for review and approval. Approval of both the protocol and the consent form must be obtained before any participant is enrolled. Any amendment to the protocol will require review and approval by the IRB before the changes are implemented to the study. All changes to the consent form will be IRB approved; a determination will be made regarding whether previously consented participants need to be re-consented.

13.3 INFORMED CONSENT PROCESS

[figure not shown]
13.3.1 CONSENT/ASSENT AND OTHER INFORMATIONAL DOCUMENTS PROVIDED TO PARTICIPANTS

Consent forms describing in detail the study agent, study procedures, and risks are given to the participant and written documentation of informed consent is required prior to starting intervention/administering study product. The following consent materials are submitted with this protocol:

- 1. Oral Study Drug Compliance Diary
- 2. CC-122 Investigators Brochure, Edition 11, May 2018

13.3.2 CONSENT PROCEDURES AND DOCUMENTATION

Informed consent is a process that is initiated prior to the individual's agreeing to participate in the study and continues throughout the individual's study participation. Extensive discussion of risks and possible benefits of participation will be provided to the participants and their families. Consent forms will be IRB-approved and the participant will be asked to read and review the document. The investigator will explain the research study to the participant and answer any questions that may arise. All participants will receive a verbal explanation in terms suited to their comprehension of the purposes, procedures, and potential risks of the study and of their rights as research participants. Participants will have the opportunity to carefully review the written consent form and ask questions prior to signing. The participants should have the opportunity to discuss the study with their surrogates or think about it prior to agreeing to participate. The participant will sign the informed consent document prior to any procedures being done specifically for the study. The participants may withdraw consent at any time throughout the course of the trial. A copy of the informed consent document will be given to the participants for their records. The rights and welfare of the participants will be protected by emphasizing to them that the quality of their medical care will not be adversely affected if they decline to participate in this study.

14 DATA HANDLING AND RECORD KEEPING

14.1 DATA COLLECTION AND MANAGEMENT RESPONSIBILITIES

Data collection is the responsibility of the clinical trial staff at the site under the supervision of the site PI. The investigator is responsible for ensuring the accuracy, completeness, legibility, and timeliness of the data reported.

14.3 PROTOCOL DEVIATIONS

A protocol deviation is any noncompliance with the clinical trial protocol, GCP, or MOP requirements. The noncompliance may be either on the part of the participant, the investigator, or the study site staff. As a result of deviations, corrective actions are to be developed by the site and implemented promptly. These practices are consistent with ICH E6:

- 4.5 Compliance with Protocol, sections 4.5.1, 4.5.2, and 4.5.3
- 4.6 5.1 Quality Assurance and Quality Control, section 5.1.1
- 4.7 5.20 Noncompliance, sections 5.20.1, and 5.20.2.

It is the responsibility of the site to use continuous vigilance to identify and report deviations within established guidelines of the Moffitt Clinical Trials office. All deviations must be addressed in study source documents. Protocol deviations must be sent to the local IRB per their guidelines. The site PI/study staff is responsible for knowing and adhering to their IRB requirements. Further details about the handling of protocol deviations will be included in the MOP.

14.4 PUBLICATION AND DATA SHARING POLICY

This study will comply with the NIH Public Access Policy, which ensures that the public has access to the published results of NIH funded research. It requires scientists to submit final peer-reviewed journal manuscripts that arise from NIH funds to the digital archive PubMed Central upon acceptance for publication.

The International Committee of Medical Journal Editors (ICMJE) member journals have adopted a clinical trials registration policy as a condition for publication. The ICMJE defines a clinical trial as any research project that prospectively assigns human subjects to intervention or concurrent comparison or control groups to study the cause-and-effect relationship between a medical intervention and a health outcome. Medical interventions include drugs, surgical procedures, devices, behavioral treatments, process-ofcare changes, and the like. Health outcomes include any biomedical or health-related measures obtained in patients or participants, including pharmacokinetic measures and adverse events. The ICMJE policy, and the Section 801 of the Food and Drug Administration Amendments Act of 2007, requires that all clinical trials be registered in a public trials registry such as ClinicalTrials.gov, which is sponsored by the National Library of Medicine. Other biomedical journals are considering adopting similar policies. For interventional clinical trials performed under NIH IC grants and cooperative agreements, it is the grantee's responsibility to register the trial in an acceptable registry, so the research results may be considered for publication in ICMJE member journals. The ICMJE does not review specific studies to determine whether registration is necessary; instead, the committee recommends that researchers who have questions about the need to register err on the side of registration or consult the editorial office of the journal in which they wish to publish.

FDAAA mandates that a "responsible party" (ie, the sponsor or designated principal investigator) register and report results of certain "applicable clinical trials":

- Trials of Drugs and Biologics: Controlled, clinical investigations, other than Phase I investigations, of a product subject to FDA regulation;
- Trials of Devices: Controlled trials with health outcomes of a product subject to FDA regulation (other than small feasibility studies) and pediatric postmarket surveillance studies.

NIH grantees must take specific steps to ensure compliance with NIH implementation of FDAAA.

